
4. Study Procedures

a. Study design, including the sequence and timing of study procedures
 (Distinguish research procedures from those that are part of routine care): Single arm proof of concept interventional study.

Specifics of each clinical visit including data collected and procedures performed are as follows:

- Baseline examination data collection consists of:
 - o Signed informed consent obtained
 - O Demographic data (age, gender, race, duration of uveitis, anatomic location of uveitis, smoking status, presence of systemic disease associated with uveitis)
 - Treatment history (current therapies for the treatment of uveitis, history of corticosteroid use including periocular corticosteroids, history of immunosuppressive drug use, need for IOP-lowering medications)
 - Past ocular history (any complications due to uveitis, any ocular surgeries or procedures, presence of amblyopia, history of glaucoma or ocular hypertension, treatment to lower intraocular pressure including laser procedures and/or surgeries
 - Ophthalmic examination including best-corrected visual acuity, IOP measurement, presence and degree of uveitis activity, presence of ocular complications including cystoid macular edema (CME), findings of slit lamp examination including presence and degree of cataract, findings of fundoscopic examination including cup to disc ratio.
 - Visual field assessment
 - O Slit lamp photos to assess cataract if eye(s) are phakic O Optic nerve photos
 - Results of baseline OCT and fluorescein angiography testing if clinically indicated NEI
 VFQ and EuroQol administered
- Dexamethasone pellet placement occurs within 14 days of baseline examination; for patients with bilaterally active uveitis, placement of a dexamethasone pellet in the second eye should occur within 14 days of the first implantation or within 30 day of the baseline examination.
 - O Adverse events related to the procedure will be collected (e.g., vitreous hemorrhage, elevated IOP, retinal detachment) at time of placement
- 1-month examination o Interval treatment history (current therapies for the treatment of uveitis, history of corticosteroid use including periocular corticosteroids, history of immunosuppressive drug use, need for IOP-lowering medications)
 - o Interval ocular history (any complications due to uveitis, any ocular surgeries or procedures, history of glaucoma or ocular hypertension, treatment to lower intraocular pressure including laser procedures and/or surgeries

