 - Ophthalmic examination including best-corrected visual acuity, IOP measurement, presence and degree of uveitis activity, presence of ocular complications including cystoid macular edema (CME), findings of slit lamp examination including presence and degree of cataract, findings of fundoscopic examination including cup to disc ratio.
 - o Results of OCT and fluorescein angiography testing if clinically indicated o NEI-VFQ and EuroQoL administered.
 - o Adverse event reporting
- 2-month examination o Interval treatment history (current therapies for the treatment of uveitis, history of corticosteroid use including periocular corticosteroids, history of immunosuppressive drug use, need for IOP-lowering medications)
 - Interval ocular history (any complications due to uveitis, any ocular surgeries or procedures, history of glaucoma or ocular hypertension, treatment to lower intraocular pressure including laser procedures and/or surgeries

- Ophthalmic examination including best-corrected visual acuity, IOP measurement, presence and degree of uveitis activity, presence of ocular complications including cystoid macular edema (CME), findings of slit lamp examination including presence and degree of cataract, findings of fundoscopic examination including cup to disc ratio.
- Results of OCT and fluorescein angiography testing if clinically indicated o NEI-VFQ and EuroOoL administered.
- o Adverse event reporting
- 3-month examination o Interval treatment history (current therapies for the treatment of uveitis, history of corticosteroid use including periocular corticosteroids, history of immunosuppressive drug use, need for IOP-lowering medications)
 - o Interval ocular history (any complications due to uveitis, any ocular surgeries or procedures, history of glaucoma or ocular hypertension, treatment to lower intraocular pressure including laser procedures and/or surgeries
 - Ophthalmic examination including best-corrected visual acuity, IOP measurement, presence and degree of uveitis activity, presence of ocular complications including cystoid macular edema (CME), findings of slit lamp examination including presence and degree of cataract, findings of fundoscopic examination including cup to disc ratio.
 - o Results of OCT and fluorescein angiography testing if clinically indicated o NEI-VFQ and EuroQoL administered.
 - o Adverse event reporting

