 - N/A. Use of the dexamethasone pellet and immunosuppressive drug therapy are each part of standard clinical care in the treatment of active intermediate and posterior uveitis. The dexamethasone pellet is FDA-approved for the treatment of intermediate and posterior uveitis.
- e. Justification for inclusion of a placebo or non-treatment group.
 - N/A. There is no placebo or non-treatment arm in this pilot study.
- f. Definition of treatment failure or participant removal criteria.
 - N/A
- g. Description of what happens to participants receiving therapy when study ends or if a participant's participation in the study ends prematurely.

- Since all treatments are currently used in the clinical care of uveitis patients, all patients enrolled in this study will be able to continue receiving therapy according to best medical judgment once the study ends.

5. Inclusion/Exclusion Criteria Inclusion Criteria:

- Active sight-threatening intermediate or posterior uveitis for which immunosuppressive drug therapy is planned and the physician is considering treatment with high-dose corticosteroid to control the uveitis whilst immunosuppressive drugs are being instituted or adjusted.
 - o Note: it is acceptable for the patient to already be on an immunosuppressive drug as long as high dose corticosteroids are indicated.
- Patients must be age 18 years or older (the dexamethasone pellet is not FDA-approved for pediatric use) and sign an informed consent.
- The ocular media must be clear enough to obtain OCT and fundus photographs.
- No elective intraocular surgery should be planned for the first 3 months after enrollment.

Exclusion Criteria:

- Infectious uveitis
- History of scleritis
- Active or suspected viral infection of the cornea or conjunctiva
- History of mycobacterial or fungal disease
- HIV positivity
- Age <18 years old
- Allergy to dexamethasone
- Uncontrolled IOP
- Advanced glaucoma
- Aphakia with rupture of the posterior lens capsule
- ACIOL with rupture of the posterior lens capsule
- Media opacity that would preclude evaluation of the posterior pole via fundus photography or OCT assessment
- Planned elective ocular surgery within 3 months of enrollment Any systemic disease requiring systemic corticosteroids.

6. Drugs/ Substances/ Devices

a. The rationale for choosing the drug and dose or for choosing the device to be used.

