 - The cumulative incidence of control of inflammation (0.5+ or less vitreous cells in the liquid vitreous; trace or less anterior chamber cells; and inactive chorioretinal lesions) at the 3month visit and the 6-month visit will be compared to the published data (from Johns Hopkins and from the SITE database) of the cumulative incidence of steroid-sparing success (prednisone <=7.5 mg daily and controlled disease) and of oral steroid discontinuation with the goal of proving NON-INFERIORITY of the dexamethasone pellet. Cumulative incidences of ocular and systemic side effects of the dexamethasone pellet will be compared to those of oral prednisone via rates and cumulative incidences at 12 months.
- c. Statistical plan including sample size justification and interim data analysis.
 - 20 patients will be enrolled and the data regarding success of control of uveitis at the 6 and 12 month examinations will be compared with historical published data. Comparative data from the Johns Hopkins cohort, SITE database, and published MUST data will be utilized. d. Early stopping rules.
- None

8. Risks

- a. Medical risks, listing all procedures, their major and minor risks and expected frequency.
 - Dexamethasone pellet insertion within 14 days of the baseline visit and potential insertion at months 3, 6, 9, and every 3 months thereafter based on the study protocol and clinical judgment of the PI/study ophthalmologist.
 - Dexamethasone pellet should not be used if patient is allergic to any of its ingredients.
 - Injections into the vitreous in the eye may be associated with eye inflammation, subconjunctival hemorrhage, and transient increased eye pressure. Rarely, intravitreal injections may be associated with vitreous hemorrhage, retinal detachment, or endophthalmitis. The risk of performing an intravitreal injection as part of this study is no greater than that associated with clinical care in the treatment of uveitis. The study ophthalmologist will monitor the patient regularly after each injection.

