 - Use of corticosteroids (including dexamethasone) may produce posterior subcapsular cataracts, increased intraocular pressure, glaucoma, and may increase the establishment of secondary eye infections due to bacteria, fungi, or viruses. However, these side effects have been reported to occur less frequently with the dexamethasone pellet than with other forms of intravitreal corticosteroids such as triamcinolone acetonide or fluocinolone acetonide. There may be a risk of the dexamethasone pellet moving into the anterior chamber of the eye in eyes in which cataract surgery has been performed. However, the risk is greatest in aphakic eyes or eyes with anterior chamber intraocular lens (ACIOL) in which the posterior capsule has been ruptured. Because of this, these eyes are excluded from this study.

- There are no major risks or discomforts associated with SD-OCT imaging, Humphrey Visual Field, visual acuity.
- Photographing of the eyes is low risk but may be uncomfortable because of the bright flashes of light used to take the pictures. The test takes about 5 to 10 minutes.
- Fluorescein angiography might cause nausea and vomiting in some patients.
- Overall, the mentioned risks above are not greater than those of standard clinical care with these patients.
- b. Steps taken to minimize the risks.
 - N/A. The risks associated with the treatment of uveitis in this study are no greater than those associated with routine care of a patient with these types of uveitis.
- c. Plan for reporting unanticipated problems or study deviations.
 - Adverse Event Reporting at each visit after the baseline visit. Which includes: Loss of three lines or greater of visual acuity, new onset cataract, new onset intraocular pressure (IOP) greater than 21 mm Hg, new onset intraocular pressure greater than 30 mm Hg, rise of IOP of 10 mm Hg or greater, need for cataract surgery, need for glaucoma surgery, complications of dexamethasone pellet insertion including, but not limited to: vitreous hemorrhage, retinal detachment and endophthalmitis.
- d. Legal risks such as the risks that would be associated with breach of confidentiality.
 - Risks to one's privacy will be addressed by collecting the data in a de-identified manner and stored in a locked office. The whole study will be conducted by JHU IRB certified research personnel based on HIPPA regulations.
- e. Financial risks to the participants.

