 - The clinical visits will be charged to the patient's insurance as they are part of the clinical standard of care. The use of immunosuppressive drug therapy and its laboratory monitoring also will be charged to the patient's insurance.
 - The dexamethasone implants are being provided by the study sponsor and therefore the patient will not incur a charge for this drug or procedure.
- All other study specific procedures such as (lens photos, visual field testing, optic disc photos will be covered by study sponsor.

9. Benefits

- a. Description of the probable benefits for the participant and for society.
 - The study participants may benefit from the treatment as all participants will be treated. We may learn of a new way to treat these type of patients that is as effective as oral prednisone but without the systemic side effects.

10. Payment and Remuneration

- a. Detail compensation for participants including possible total compensation, proposed bonus, and any proposed reductions or penalties for not completing the protocol.
 - Participants will receive \$15.00 at each visit, to compensate their parking charge.

11. Costs

- a. Detail costs of study procedure(s) or drug (s) or substance(s) to participants and identify who will pay for them.
 - Costs of procedures done only for the study are covered by the research funding from the study sponsor. The study participant and/or their insurance company will be responsible for the cost of the regular medical care, in the same manner as if the participant was not participating in this study.

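### Section 7b promises a 12-month systemic side effect comparison with oral prednisone, but the plan names no systemic event, gives no method of eliciting one, and records no existing ones at baseline

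*Combined protocol and SAP*

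**What the plan says.** The secondary outcomes in section 7b include this comparison: "Cumulative incidences of ocular and systemic side effects of the dexamethasone pellet will be compared to those of oral prednisone". The measures are rates and cumulative incidences at 12 months. The prednisone side of the comparison is external, since the study has one arm. On sources, section 7c says: "Comparative data from the Johns Hopkins cohort, SITE database, and published MUST data will be utilized". It does not say which of the three supplies side effect rates or definitions.

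Section 8c sets the timing and gives the only list of events: "Adverse Event Reporting at each visit after the baseline visit. Which includes: Loss of three lines or greater of visual acuity, new onset cataract", followed by further ocular items. In section 4a, the examinations at months 1, 2, 3, 6, 9 and 12 each carry the line "Adverse event reporting" without further instruction.

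The 4a baseline list covers drug exposure, "Treatment history (current therapies for the treatment of uveitis, history of corticosteroid use including periocular corticosteroids, history of immunosuppressive drug use", and one systemic item, "presence of systemic disease associated with uveitis". It also includes EuroQol. Section 5 admits patients with "Active sight-threatening intermediate or posterior uveitis for which immunosuppressive drug therapy is planned". Section 9a describes what might be learned as a treatment "as effective as oral prednisone but without the systemic side effects".

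**The concern.** A cumulative incidence needs a defined event, a way of detecting it, and a baseline that shows who is still at risk. The ocular half of the 7b sentence has these: ocular history, pressure measurement, visual fields and photographs at baseline, and numerical thresholds in 8c. The systemic half has none of them in writing.

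Avoiding the systemic effects of prednisone is the reason the study gives for trying the pellet, in the background and again in 9a. If the plan is followed as written, a count of whatever patients volunteer, with no baseline to subtract, would be set beside published prednisone rates that may have been defined and gathered differently. Such a comparison could not be interpreted in either direction.

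**Working it through.** The plan gives no event rate, margin, alpha or power for this comparison, so there is no figure to reproduce. The check is a reading of the plan, followed by arithmetic to show scale.

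**1. Definition.** Events named in 8c: visual acuity loss of three lines or more; new cataract; pressure above 21 mm Hg; pressure above 30 mm Hg; pressure rise of 10 mm Hg or more; cataract surgery; glaucoma surgery; vitreous hemorrhage; retinal detachment; endophthalmitis. That is 10 named, 0 systemic. The open-ended phrase near the end of the list attaches to complications of pellet insertion.

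**2. Elicitation.** Follow-up items in 4a are treatment history, ocular history, ophthalmic examination, imaging, two questionnaires and the open adverse event line. There is no interval medical history, checklist or laboratory item. Laboratory monitoring of immunosuppressive drugs appears only in 8e, as a charge to insurance.

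**3. Baseline.** The list records exposure to corticosteroids and immunosuppressants, but not their existing effects. Uveitis-associated systemic disease is a different item. EuroQol is not designated as a side effect measure. Adverse event reporting begins after this visit.

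**4. Scale.** The only input from the documents is n = 20.

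- One patient misclassified: 1/20 = 5 percentage points.
- Failure to ask: if a fraction s of true events is recorded and the true incidence is p, the chance of recording none is (1 − ps)^20. With p = 5% and s = 1 it is 0.95^20 = 36%. With p = 10% and s = 1 it is 0.90^20 = 12%. With p = 10% and s = 0.5 it is again 0.95^20 = 36%. These values of p and s are assumptions. A zero count is equally likely under a 5% incidence fully recorded and a 10% incidence half recorded.
- Baseline status: assume that 4 of 20 patients have an item at entry and 2 of the other 16 develop it by month 12.

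| How the item is counted | Recorded incidence |
|---|---|
| New events among those at risk | 2/16 = 12.5% |
| New events over all enrolled | 2/20 = 10% |
| Existing effects counted as new | (4 + 2)/20 = 30% |
| Nothing asked and nothing volunteered | 0/20 = 0% |

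The error can run either way, and the documents do not show which way is likelier.

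**5. Precision, a separate matter.** Exact two-sided 95% intervals at n = 20 are: 0/20, 0 to 16.8% (upper limit 1 − 0.025^(1/20)); 1/20, 0.1 to 24.9%; 2/20, 1.2 to 31.7%; 5/20, 8.7 to 49.1%. They reflect the sample size and would be the same with perfect definitions, so they do not measure this gap.

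**The case against.** The strongest reply is that the plan does collect adverse events at every follow-up visit and does not restrict them to the eye. The 8c list is introduced as inclusive, and 8c is a plan for reporting problems and deviations, not the definition of a 7b outcome. A reader might infer from the ten ocular items that no systemic data will be collected at all. The documents do not support that: systemic events can be reported spontaneously. What stands is that none is named and no method of asking is given.

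Second, a reader might infer that the missing information would be lost for good. That is also too strong. The visits are part of clinical care and immunosuppressive drugs are monitored, so records may recover some onset dates and baseline conditions. The plan does not say they will be used, and their completeness is unknown. Section 5 also excludes systemic disease requiring systemic corticosteroids, which removes one source of existing steroid effects but not earlier treatment for the uveitis itself.

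Third, difficulty in attributing events is common to any single-arm study of an added treatment, and the full name of the SITE group in 7a suggests that at least one named source concerns immunosuppressed patients. Both points are fair. They leave 7b's phrasing as a matter of wording: with immunosuppression planned for every patient, the single arm cannot show which events belong to the pellet.

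Finally, this is one clause of a secondary outcome in a 20-patient proof of concept study, with no decision rule attached. That limits the importance but does not remove the gap.

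**Conclusion.** The concern holds in limited form. The plan commits to a systemic comparison and supplies only open reporting after baseline, without systemic definitions, a method of elicitation, or a record of existing effects. The result as planned could not separate few events from few questions, or new effects from old ones, and may not match the external prednisone rates.

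A reader might go further and infer a bias in favour of the pellet. The documents do not support that: missed events would lower the count and existing effects counted as new would raise it. The size is unknown beyond 5 points per misclassified patient, taking all 20 as the denominator. Control of uveitis, the primary outcome, is untouched. Importance is low to moderate. The conclusion assumes that no unpublished form or manual already supplies the missing items; the documents mention none.

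**What to change.** - **7b:** name which 7c source supplies the prednisone side effect rates. Use its event definitions and its counting rule, whether all events or only those attributed to treatment. Limit the items to those obtainable by interview or from existing records.
- **4a:** add a short checklist of those items to the baseline examination and to each existing follow-up visit, with onset date. Cross-refer to it from 8c, which covers only visits after baseline.
- **Analysis:** for each item, report the 12-month cumulative incidence among patients free of that item at baseline. Give an exact 95% interval if follow-up is complete, or a time-to-event estimate if it is not. Report also the rate that 7b already plans.
- **Wording:** describe the result as incidence under pellet plus immunosuppression, not as an effect of the pellet alone.
- **Otherwise:** delete the systemic part of the 7b comparison and draw no systemic conclusion.

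The cost is one short form and a few minutes per existing visit. Some items the source reports may have to be left out. The systemic rate may look less favourable once patients are asked. The estimate stays imprecise and non-randomised: 0/20 still has an upper limit of 16.8%, and removing patients who already have an item widens it (0/16, if 4 were removed, gives 1 − 0.025^(1/16) = 20.6%).
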